13.0 Study Organization and Governance

PRIDE will be conducted at two Clinical Centers with extensive experience in recruitment of obese and overweight persons and in administering successful weight reduction programs (The Miriam Hospital/Brown Medical School and the University of Alabama). The trial will be coordinated at the Women's Health Clinical Research Center at the University of California, San Francisco. The Steering Committee will be the primary governing body of the study and will be comprised of the Principal Investigators from the Clinical Centers, a behavioral consultant from the University of Arkansas, the Principal Investigator and Co-Principal Investigator of the Coordinating Center and project scientists from

NIDDK. In the development stage of PRIDE, the Steering Committee will direct refinement of the study design, completion of the protocol, and development of interventions, operations manual and data collection forms. As recruitment and enrollment begin, the Steering Committee will monitor study progress and quality, and resolve issues that arise during follow-up. Finally, the Steering Committee will review and approve proposals for ancillary studies, analyses, scientific presentations and manuscripts.

A Data and Safety Monitoring Board (DSMB) will be organized by the Project Office of the NIDDK. The DSMB will convene at the end of protocol development to review the protocol and develop guidelines for DSMB activities and stopping rules. They will meet 6 months after recruitment begins then approximately annually to review study progress, oversee participant safety, monitor data quality, and provide operational and technical advice to the Steering Committee and the NIDDK project officer. The DSMB will be comprised of five members with expertise in operational and biostatistical aspects of clinical trials, urinary incontinence and weight reduction. No member of the DSMB will participate in the study as an investigator or be involved in any way in the conduct of the study.

LITERATURE CITED

1.0 BACKGROUND AND RATIONALE

Urinary incontinence is a prevalent health condition in women and has a significant impact on quality of life. Over 13 million Americans, including 25% of reproductive age women and up to 50% of postmenopausal women, are affected by stress (involuntary loss of urine with coughing, sneezing, straining, or exercise), urge (loss of urine associated with a strong need or urge to void) or mixed incontinence (episodes of both types).¹⁻³ Epidemiological studies suggest that obesity is a strong risk factor for urinary incontinence⁴⁻⁷ and early observational^{8, 9} and small cohort studies^{10, 11} suggest that weight reduction may be an effective treatment for incontinence.

PRIDE — The **Program to Reduce Incontinence by Diet and Exercise** is a multicenter, randomized, clinical trial evaluating weight reduction as an innovative treatment for urinary incontinence in 330 overweight and obese women with incontinence. Women will be randomized to either a 6-month behavioral weight reduction program or control (instructional handouts and brief informational sessions on diet and exercise) and followed for 18 months. At baseline, all women will be given a pamphlet describing a self-administered behavioral treatment program for incontinence. **In a subgroup of 100 women, we will perform standardized pelvic floor evaluation and urodynamic studies at baseline and at 6 months to elucidate the mechanism by which weight loss improves incontinence.**

2.0 CLINICAL TRIAL OBJECTIVES

The primary aims of PRIDE are:

1. to determine whether randomization to a weight reduction program results in greater reductions in frequency of incontinence episodes at 6 months compared to control;
2. to identify women who are most likely to experience improved continence after weight reduction, based on factors such as initial body mass index, body fat distribution and type of incontinence (stress, urge or mixed).

As a part of PRIDE we plan to:

1. conduct exploratory analyses to evaluate whether baseline urodynamic measures can identify women who are most likely to experience improved continence after weight reduction and;
2. investigate the mechanism by which weight loss improves continence by examining the relationship of improvement in continence and changes in urodynamic measures.

CONFIDENTIAL

To achieve these aims, the pelvic floor evaluation and urodynamic testing (UDS) will be performed on the first 50 volunteers at each site who agree and sign a separate informed consent. Standardized urodynamic testing will take place at baseline and again at the 6-month follow-up study visit.

3.0 STUDY DESIGN

100 overweight or obese women with urinary incontinence will undergo pelvic floor evaluation and urodynamic testing at baseline and at 6 months, following completion of either the 6-month weight reduction program or control. Women participating in PRIDE will be randomized in a 2-to-1 ratio to either of these treatment groups and it is expected that the randomization pattern will be reflected in the Urodynamic Substudy. (Please see the PRIDE Protocol for a complete description of the PRIDE study.)

3.1 STUDY TIMELINE

The first year of the study will include developing and refining the protocols, operations manual, forms, database, intervention materials and websites. Participant recruitment will begin in the first year and continue for approximately two years. The UDS evaluations will begin in year 2.

4.0 STUDY SITES

The study will be conducted at two clinical centers and three institutions: Miriam Hospital and Brown University, Providence, RI and the University of Alabama, Birmingham, AL. Data will be collected, managed and analyzed at the Women's Health Clinical Research Center, University of California at San Francisco, San Francisco, CA. A list of investigators is available at the PRIDE public website at: <http://coordinatingcenter.ucsf.edu/pride/>

5.0 STUDY POPULATION

5.1 SAMPLE SIZE

Of the 330 volunteers for PRIDE, the first 100 women who agree to participate in the Urodynamic Study will be enrolled (approximately 50 at each of 2 clinical centers).

5.2 INCLUSION AND EXCLUSION CRITERIA

CONFIDENTIAL

All participants must first meet the entry criteria for PRIDE and must sign an additional informed consent form for the Urodynamic Study. Because of weight limits for the urodynamic testing chairs and difficulty performing the evaluation in very obese women, participants with weight < 300 pounds are eligible for this sub-study.

6.0 ETHICS

6.1 INSTITUTIONAL REVIEW BOARD

The study protocol, informed consent form, study questionnaires, educational and recruitment materials must be approved by the Institutional Review Board at each institution prior to the start of the study. Protocol amendments generated during the study must be approved by the IRBs prior to their implementation. Copies of all IRB approval letters will be sent to the Project Office at the NIDDK. Reports issued by the PRIDE Data and Safety Monitoring Board will be distributed to the investigators to be forwarded to their IRBs. Any serious adverse events that occur during the trial must be reported to each IRB.

6.2 INFORMED CONSENT FORM

The UDS informed consent form will explain in lay language the goals of the substudy, the visits and procedures and the risks and benefits of participating. Any amendment to the protocol generated during the study that impacts participants will be reflected in a revised consent form that must be signed by the participant.

7.0 STUDY SCHEDULE AND PROCEDURES

7.1 ENROLLMENT PROCEDURES

7.1.1 Enrollment in the UDS substudy

Women enrolling in PRIDE will be randomly allocated in a 2-to-1 ratio to either the weight reduction program or control condition. Prior to randomization, women will be asked to participate in the UDS substudy. A volunteer sample will be included. After the first 30 women are enrolled in the UDS substudy, we will evaluate the sample to assess the distribution of group assignment (weight loss or control condition), incontinence type and BMI. We will classify incontinence type as 1) stress only or mixed stress incontinence

CONFIDENTIAL

and 2) urge only or mixed urge incontinence. Our goal is to have a UDS substudy sample with approximately 67% women in the weight loss group, 50% with stress/mixed stress incontinence, and 50% with BMI < 35 kg/m². If there is >10% deviation from these goals, we will consider limiting enrollment in the UDS study to underrepresented intervention group, incontinence type or BMI category.

7.1.2 Ensuring Objective Assessments

Throughout the study every effort will be made to ensure objective and blinded assessments of outcomes. Staff who performs urodynamic studies will not be informed of the participant's treatment assignment. Care will be taken to avoid overtly identifying the treatment assignments on participant charts.

7.2 STUDY VISITS

7.2.1 Recruitment

All women who are eligible and agree to participate in PRIDE will be offered the option of undergoing pelvic floor evaluation and urodynamic testing. The UDS substudy will be explained fully after the woman has completed her second screening visit. Those who agree to participate will be scheduled for a UDS visit in addition to the main study baseline visit.

7.2.2 Urodynamic Study Visits

At the baseline and at the 6 month urodynamic visits, a urogynecologist, or a designee under her supervision, will perform the pelvic floor evaluation using the Brink's score of pelvic muscle strength, Pelvic Organ Prolapse Quantification (POP-Q), and urethral hypermobility (Q-tip test) and the urodynamic studies including cough stress test, passive uroflowmetry and filling cystometrogram,. Measurements, diagnoses, and terms will conform to the recommendations of the Committee on Standardization of Terminology of the International Continence Society and will use the same methods as the National Institute of Diabetes and Digestive and Kidney Diseases (NIDDK) Urinary Incontinence Treatment Network studies.¹²

7.3 URODYNAMIC STUDY PROCEDURES

CONFIDENTIAL

Urinalysis. A urine dipstick test for urinary tract infection will be done prior to the pelvic floor evaluation and UDS procedures. When there is suspicion for infection, the remainder of the urodynamic substudy evaluation will be postponed until the infection has been treated.

The Brink's test assesses pelvic muscle strength by scoring perceived pressure on the examiner's finger, alteration of the vertical plane, and contraction time.¹³ Using sterile gloves and lubricant jelly the examiner inserts one or two fingers into the participant's vagina and instructs the participant to squeeze the pelvic muscles. Any degree of flicker on the examiner's finger(s) is considered evidence of ability to contract the muscle. This test will assess three elements of the pubococcygeus muscle contraction: pressure, duration (using a stop watch that is accurate to the tenth of a second), and displacement.

The Pelvic Organ Prolapse Quantification (POP-Q) is a standardized description of the severity of pelvic organ prolapse with good inter- and intra-observer reliability for prolapse staging.¹⁴⁻¹⁷ This procedure will be performed according to the guidelines established by the International Continence Society¹⁸ and will be standardized as demonstrated in a videotape produced by Duke University Medical Center ("Pelvic Organ Prolapse Quantification Exam"). Any prolapse will be noted and the maximum anterior-posterior length with maximum straining of the genital hiatus and perineal body will be measured and recorded. The six primary measuring points are defined in the International Continence Society's standardization report and a detailed description is included in the PRIDE Operations Manual. Total vaginal length will be recorded.

The Q-tip test will be used to evaluate mobility of the urethra and bladder neck. A sterile, lubricated cotton or dacron swab (Q-Tip) is placed into the urethra until it lies just within the urethrovesical junction. The angle circumscribed by the distal end of the swab relative to the horizontal at rest and during maximum Valsalva effort is measured with a Robinson Pocket goniometer. Bladder neck hypermobility is defined as a resting angle $>30^\circ$ or maximum straining angle $>30^\circ$.^{19, 20}

The Cough Stress Test will be performed to determine the presence and degree of stress incontinence. Stress tests that are positive in the face of positive urine cultures will be repeated when the infection is resolved. After the participant voids, the bladder is emptied completely using a 12 French catheter. Then the bladder is retrograde gravity filled to 300 ml or maximum capacity, whichever is less and the catheter is removed. In the supine position, the participant is asked to Valsalva and cough. If no

CONFIDENTIAL

leaking is noted, the participant stands and is asked to Valsalva and cough. Participants with Stage III or IV anterior prolapse who have a negative cough stress test (do not leak) will have their prolapse reduced (instructions detailed in the PRIDE Operations Manual) and provocative maneuvers will be repeated. Stress incontinence is considered present when the participant demonstrates transurethral urine leakage with or immediately after increased intra-abdominal pressure (with Valsalva effort or coughing).

Non-Instrumented Uroflowmetry (NIF) is performed after the 300 cc cough stress test to measure maximum urine flow rate, mean flow rate, time to maximum flow, and voided volume. Any of the electronically derived methods of calculating the uroflowmetry values are acceptable. The uroflowmeter should be calibrated in accordance with routine clinical site practice standards and the scale should be set to zero prior to the start of each participant's study. The participant will void into the uroflowmetry machine while in the sitting position on the Uroflow chair and a time-flow curve is recorded using a standard urodynamic recorder. Flow pattern is classified as either normal (continuous, smooth and arc shaped with high amplitude) or abnormal (doesn't meet these criteria). Post-void residual (PVR) volume will be measured with a catheter.

A Filling Cystometrogram (CMG) will be performed to measure intravesical pressure (Pves), intra-abdominal pressure (Pabd), and subtracted detrusor pressure (Pdet). With the participant sitting in a 45 degree reclined position, the fluid-filled column-type tubing will be connected to a dual lumen 8 French catheter. An intravesical catheter will be placed and the bladder filled with room temperature saline or sterile water at a rate of 50 ml/min. A rectal catheter will be used to measure continuous intra-abdominal pressure. Pressures will be continuously recorded on a multichannel urodynamics recorder throughout the conduct of the CMG. Flow rate and volume will also be recorded continuously.

Bladder Sensation Parameters: Three bladder sensation parameters will be measured during filling cystometry. The participant is instructed to state when she has the sensation of 1) first desire to void, 2) strong desire to void, and 3) sensation of maximum cystometric capacity, using standardized definitions/descriptions.

To assess proper placement of catheters the participant is instructed to cough at various times during the cystometrogram and the examiner will then record the Valsalva Leak Point Pressure (VLPP) or absolute intravesical pressure during the Valsalva maneuver that produced leakage.

CONFIDENTIAL

Procedures will differ slightly according to the presence or absence of Stage III or IV anterior prolapse and examiners will follow instructions detailed in the PRIDE Operations Manual.

The following data points for the CMG will be calculated by the UCSF Coordinating Center for each participant prior to analyses:

- Bladder compliance [*Maximum Cystometric Capacity (MCC) / (Pves at MCC - Pves at baseline)*]
- Mean of VLPP values obtained for unreduced and reduced measurements
mean Pves = (Pves 1 + Pves 2 + Pves 3) / 3 or mean Pves = (Pves 1 + Pves 2) / 2
- VLPPs from different baselines with and without reduction (*mean Pves - Pves at baseline*)

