11.0 STATISTICAL ANALYSIS

This will be an exploratory analysis of potential mechanisms for improvement in incontinence with weight loss. A series of closely related mixed linear models will be used to assess mechanisms by which the weight loss intervention potentially affects measured incontinence frequency as well as related quality of life measures. We will first assess modification of the effects of treatment by baseline urodynamic measurements of leak point and intravesical pressures, to determine if the effectiveness of the weight loss intervention varies by these parameters. To maximize efficiency, effect modification will be assessed as a continuous interaction between treatment assignment and the urodynamic measures. We will then examine the overall

CONFIDENTIAL

effects of assignment to the weight loss arm on the urodynamic measures as well as weight loss, to show the effect of the intervention on the proposed mediators. Next, we will use repeated measures models to determine the association between change since baseline in the proposed mediators and current incontinence frequency, to show that changes in the mediator are associated with changes in the primary outcome, and to determine which of the proposed mediators independently predict change in incontinence frequency. Finally, we will examine the attenuation of the estimated effect of treatment on incontinence frequency after controlling for changes in the proposed mediators, as an estimate of the proportion of the treatment effect explained. Confidence intervals for proportion of the treatment effect explained will be computed.²²

CONFIDENTIAL

LITERATURE CITED

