Insert the transurethral and rectal balloon catheters. Instruct the participant to cough to assess proper placement of the catheters and to document the dynamic response of the pressure channels. The Pves and Pabd signals (tracings) should demonstrate good tracking and the Pdet should be between 0 and 5 cm/H₂O at this time. If not, the catheters should be flushed, their position should be evaluated and other troubleshooting measures taken. A negative Pdet reading should also prompt immediate troubleshooting. Excessive rectal balloon filling may cause abnormally high Pabd readings and the balloon volume may need to be adjusted. Filling should commence when Pabd and Pves pressure signals document the dynamic response of the pressure channels and the Pdet is between 0 and 5 cm/H₂O.

Document Pves and Pabd at baseline with an annotation line on the signals (tracing).

At a bladder volume of 100 ml, instruct the participant to cough and reassess proper placement and function of the catheters and transducers (**annotate this cough on the signal**). Look for the dynamic response of the pressure channels. If pressures channels do not track at this time, repeat troubleshooting measures.

Bladder Sensation Parameters: Three bladder sensation parameters should be measured during filling cystometry. The participant should be instructed to state when she has the sensation of 1) first desire to void, 2) strong desire to void, and 3) sensation of maximum cystometric capacity, using the following standardized definitions/descriptions.

First Desire to Void: When filling commences, instruct the participant that you need to know when she has a *first desire to void*. This is defined as “the feeling, during filling cystometry that would lead the participant to pass urine at the next convenient moment, but voiding can be delayed if necessary”. Tell the participant:

“If you are watching TV, tell me when you would go to the bathroom at the next commercial.”

Strong Desire to Void: After this milestone is reached, instruct the participant that you need to know when she has a *strong desire to void*. This is defined as “a persistent desire to void without the fear of leakage.” Tell the participant:

“Tell me when you can’t wait for the next commercial.”

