- **If “reduced” VLPPs cannot be obtained at 200ml, maintain the reduction** and repeat Valsalva and maximal cough maneuvers at successive 100ml increments until leakage occurs or MCC is reached. Both the Valsalva and maximal cough maneuvers should be done at 100 ml increments until leakage occurs OR MCC is reached. If the participant doesn’t leak at MCC with Valsalva maneuvers, instruct her to cough maximally, described above, and observe for urine leakage. If leakage is not observed, remove the transurethral catheter and instruct her to cough maximally while you observe for urine leakage. If leakage is still not observed, remove the prolapse reduction, instruct the participant to stand, repeat a maximal cough, and observe for urine leakage. If leakage is still not observed, reduce the prolapse and repeat the maximal cough testing. Record no loss or loss (and volume) on data form. Record the presence or absence of urodynamic stress incontinence at MCC.

Regardless of the volume at which the participant leaks, the bladder volume at first desire to void, strong desire to void, and MCC should be determined and annotated on the signals. The **Pves and Pabd at MCC** should also be annotated.

If micturition of > 100 ml occurs or >100 ml is otherwise lost during the performance of CMG, the test should be re-started after completely emptying the bladder to ensure accurate bladder volumes.

All critical data points should be annotated on the signals.

If the PVR following NIF is > 150 ml, have participant void and repeat PVR. Record on the NIF Data Form as Measured PVR #2. If the repeat PVR is not done, leave the data field blank.

CMG Data Points

For every participant: The following data points for the CMG will be

obtained for **every** participant and recorded on the CYSTOMETOGRAM (CMG) AND LEAK POINT PRESSURE (LPP) form.

- Catheter diameter
- Pves at baseline (cm/H₂O)
- Pabd at baseline (cm/H₂O)
- Bladder volume at first desire to void (ml)
- Bladder volume at strong desire to void (ml)
- Prolapse status (Stage III or IV anterior prolapse – yes or no)
- Leakage with valsalva (yes or no) – to code this as “yes”, leakage must occur with valsalva at least twice at the same volume)
- Bladder volume at leakage with valsalva (ml)
- Pves at leakage (VLLP) [two measures are required]
- Bladder volume at MCC (ml)
- Leakage with cough and bladder volume at leakage
- Pves at MCC (cm/H₂O)
- Pabd at MCC (cm/H₂O)

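### Bladder compliance is derived from the change in total intravesical pressure, so any change in abdominal pressure during filling is counted as bladder stiffness in an exploratory urodynamic variable

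*Protocol*

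**What the plan says.** Section 7.3 of the urodynamic substudy protocol describes a filling cystometrogram that is to "measure intravesical pressure (Pves), intra-abdominal pressure (Pabd), and subtracted detrusor pressure (Pdet"). It adds: "A rectal catheter will be used to measure continuous intra-abdominal pressure". Among the derived cystometrogram variables, which "will be calculated by the UCSF Coordinating Center for each participant prior to analyses", bladder compliance is given as "Maximum Cystometric Capacity (MCC) / (Pves at MCC - Pves at baseline"). Both copies of the substudy protocol in the document carry this formula, and the Operations Manual repeats it in section 11.2.2.2 under the calculated data points, so it is not a misprint.

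The data-point list in section 11.2.2.2 of the Operations Manual requires "Pabd at baseline", and likewise Pabd at maximum cystometric capacity (MCC), for every participant. Neither enters any of the three listed calculated variables. Section 11.2.2.1 uses detrusor pressure as its check before filling begins: "the Pdet should be between 0 and 5" cm H2O.

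Section 11.0 of the substudy protocol names as effect modifiers "baseline urodynamic measurements of leak point and intravesical pressures". It then plans to examine "effects of assignment to the weight loss arm on the urodynamic measures as well as weight loss". Compliance is not mentioned by name.

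**The concern.** Compliance is meant to describe the bladder: how much volume it accepts per unit of pressure rise. A bladder catheter also registers whatever pressure the abdomen transmits, and the rectal catheter is there so that this part can be subtracted. The plan measures the abdominal part, uses the subtracted pressure to check its signals, and then leaves the subtraction out of the one derived variable that describes bladder wall behaviour.

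The two readings are not taken under identical circumstances. Baseline precedes filling. MCC comes after Valsalva and cough manoeuvres at 200 ml, repeated at each further 100 ml if no leakage is seen, and at a volume where the participant can no longer delay voiding. Equal abdominal pressure at both readings is possible but cannot be assumed. At stake is the interpretability of compliance in a substudy whose purpose is to explore mechanism: a variable that mixes bladder and abdominal changes cannot tell the two apart.

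**Working it through.** The plan gives no compliance value, MCC or pressure at MCC, so there is no figure to reproduce. The check is algebra on the plan's definitions, followed by an illustration over assumed values.

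**Step 1: definitions.** Pdet is the subtracted pressure (substudy protocol 7.3), so Pdet = Pves − Pabd and Pves = Pdet + Pabd.

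**Step 2: the stated denominator.** Let d denote the value at MCC minus the value at baseline.

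Pves(MCC) − Pves(baseline) = dPdet + dPabd

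**Step 3: distortion factor.**

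Stated compliance = MCC/(dPdet + dPabd) = (MCC/dPdet) × dPdet/(dPdet + dPabd)

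The factor does not depend on MCC. A rise in Pabd makes the bladder look stiffer; a fall makes it look more compliant.

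**Step 4: a constant Pabd cancels.** With MCC 400 ml and dPdet 10, take Pves at baseline as 40 and then as 30 cm H2O, with Pabd unchanged during the test: 400/(50 − 40) = 40 and 400/(40 − 30) = 40. Only a change within one test matters.

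**Step 5: size.** Assumed: MCC 400 ml; dPdet 5, 10 or 15 cm H2O; dPabd from −5 to +10 cm H2O. Entries are the stated formula, 400/(dPdet + dPabd), in ml/cm H2O. The dPabd = 0 column equals the detrusor-based value.

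| dPdet | dPabd −5 | −2 | 0 | +2 | +5 | +10 |
|---|---|---|---|---|---|---|
| 5 | undefined | 133.3 | 80 | 57.1 | 40 | 26.7 |
| 10 | 80 | 50 | 40 | 33.3 | 26.7 | 20 |
| 15 | 40 | 30.8 | 26.7 | 23.5 | 20 | 16 |

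Across each row the bladder is the same. For dPdet = 10 the factors are 2.0, 1.25, 1, 0.83, 0.67 and 0.5. The effect is largest when the detrusor rise is small.

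**Step 6: the detrusor-based form.** MCC/[(Pves − Pabd) at MCC − (Pves − Pabd) at baseline] = MCC/dPdet. For dPdet = 10 this is 400/10 = 40 whatever dPabd is. All five inputs (MCC, and Pves and Pabd at both points) are on the required data-point list.

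**The case against.** The strongest reply is that little depends on this variable. Section 11.0 calls the analysis exploratory and does not name compliance. Section 11.1 of the Operations Manual, listing baseline measures of interest, gives intravesical pressures, Valsalva leak point pressures and detrusor instability as examples, again without compliance. The substudy covers about 100 volunteers and neither primary aim uses it. All of this stands and limits the importance of the point. Compliance is nevertheless one of the few variables the plan commits to calculating for each participant, and it falls within the general reference to urodynamic measures.

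Second, the procedures limit the artefact. The 45-degree position is checked with a goniometer, both pressures are zeroed to atmosphere, tracking is checked by cough before filling and at 100 ml, and artefactual points are not to be recorded. These steps improve signal quality; they do not remove a genuine rise in abdominal pressure.

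Third, a reader might infer that the formula would make compliance appear to change with weight loss. The documents do not support that. A resting abdominal pressure altered by body weight cancels in the baseline subtraction. Nothing in the documents links changes in Pabd during filling to weight or arm, and urodynamic staff are not told the assignment. The expected consequence is noise rather than bias between arms.

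Fourth, the alternative has costs. Section 11.2.2.1 warns that an overfilled rectal balloon can give falsely high Pabd readings. A constant offset of that kind would cancel, but an unstable rectal signal would not. A reader might also expect subtraction to remove extreme values. It does not, because a detrusor change near zero has the same effect.

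Finally, the plan follows external urodynamic standards that are not reproduced in it, so a deliberate choice of Pves cannot be ruled out. No reason for it is stated.

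**Conclusion.** The point holds as a minor derivation flaw. On the plan's own definitions, the stated compliance equals the detrusor-based value multiplied by dPdet/(dPdet + dPabd). For an assumed detrusor rise of 10 cm H2O, a 2 cm rise in Pabd lowers the value by about 17% (40 to 33.3), a 10 cm rise halves it, and a 5 cm fall doubles it. These sizes rest wholly on assumed pressures; how much Pabd shifts between baseline and MCC in this population is not documented.

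The consequence is mainly measurement error in an exploratory variable that the analysis section does not name. The primary outcome is unaffected, and bias related to weight or treatment arm is not demonstrated. Because Pabd is recorded at both points, the detrusor-based value remains recoverable from the stored data.

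**What to change.** In section 7.3 of the urodynamic substudy protocol and in the calculated data points of Operations Manual section 11.2.2.2, have the Coordinating Center calculate

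compliance = MCC / [(Pves at MCC − Pabd at MCC) − (Pves at baseline − Pabd at baseline)]

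and keep the Pves-based version as a secondary description. No new measurement, form or visit is needed; one derivation line changes in each place.

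The trade-off should be recorded alongside: the value then depends on the quality of the rectal signal, and a denominator near zero or negative can still produce extreme or uninterpretable values, so the handling of such cases should be set before the variable is calculated.
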